1.4.3. Exclusion criteria

A potential subject who meets any of the following criteria will be excluded from participation in this study:

- History of concurrent clinically significant medical illness (not directly attributable to RSV infection) including but not limited to, cardiovascular, respiratory, renal, gastrointestinal, haematology, neurology, endocrinology, immunology, musculoskeletal, oncological or congenital disorders, as judged by the investigator.

Specifically excluded examples include, but are not limited to:

- Known congenital or acquired immunosuppression
- Bronchopulmonary dysplasia/chronic lung disease of infancy
- Congenital heart disease
- Down syndrome
- Prematurity, defined as gestational age <37 weeks at birth
- History of receipt of medication to treat RSV infection (e.g. ribavirin)
- Prior exposure to an RSV investigational vaccine or medication.
- History of receipt of immunoglobulin or monoclonal antibodies (including palivizumab).
- Use of steroids or montelukast within 7 days of enrolment in the study.
- Participation in another clinical study for an investigational drug within 12 weeks before entry into this study
- Parents not able to understand and communicate in the local language or English.

1.4.4. Sample size calculation

This study is a follow-up study of the RESCEU infant studies. Biomarker analysis of these samples is currently ongoing. Therefore, accurate sample size calculations are not yet possible. We will use the following considerations to select the sample size: For external validation of the biomarkers ideally a representative sample of patients independent of the development set will be used, large enough to detect potentially relevant differences between groups with sufficient precision, taking into account the observed differences between the groups in the previous studies, and the potential clinical relevance of identified differences. Given the observational case-control design, ideally the sample size would allow for adjustment for the pre-specified relevant demographic and clinical confounders. Repeated sampling within subjects will allow for estimation of within patient variation over time and may increase precision of between-group estimates. With 40 cases and 40 controls the chance is

high to verify a (true) biomarker with a reasonable combination of attributes, expressed in the fraction of cases expressing the biomarker and the separation between cases and controls (Figure 1). Therefore, the sample size of PROMISE is sufficient because we have even 3 populations of distinct severity with 40 children per group plus a healthy control population.

[figure not shown]

Figure 1. Validation: Probability of Biomarkers Successfully Passing Verification Stage (12).

2. Methods

2.1. Study parameters/endpoints

2.1.1. Main study parameter/endpoint

The primary endpoint is disease severity of RSV infection in the first year of life. The use of biomarkers that are associated with severe RSV infection and respiratory sequelae will be validated.

2.1.2. Secondary study parameters/endpoints

1. Values of biomarkers in the upper and lower airways of children with RSV infection and comparison with the values of these biomarkers in blood
2. Performance of currently used case definitions and severity measures for RSV infection in infants
3. Risk factors for severe RSV disease
4. Long-term sequelae of RSV infection in the first year of life

2.2. Study procedures

2.2.1. Main study parameter/endpoint

Participants are recruited at the moment of acute respiratory infection in hospital, at the emergency department, or GP offices.

In hospital setting (inpatient and outpatient department, emergency department):

Potential participants for the study will be identified by clinical research staff. A member of the paediatric clinical research team will identify any potentially eligible participants by attending doctor's handovers, talking to the clinical staff in hospital departments and/or screening hospital computer systems. Potential participants are informed about the study by a member of the clinical team. If parents are interested in participating in the study, a member of the study team will provide verbal and written information about the study. Medical records will be screened to confirm eligibility for inclusion, either after full consent has been received or with verbal permission from the parent/guardian/legally authorised representative. If the potential participant's RSV status cannot be determined from the medical records, written consent will be sought to perform a bedside test to assess for eligibility.

In community setting (general practitioners office):

Potential participants for the study will be identified by the general practitioner during consultations. Potentially eligible and interested participants are referred to the clinical research staff by the general practitioner. A member of the research team will contact the parents/legal guardians of potentially candidates and will explain the study. If they are expressing an interest, written consent will be sought to perform an RSV point of care test to assess for eligibility.

Healthy control infants will be identified in hospital. Patients who are in hospital for minimal invasive elective surgery procedures which are not considered to have an effect on the general health of the infant (for example correction of inguinal herniation, orchidopexy, correction of polydactyly etc) or regular check-up which requires the drawing of blood are identified by attending doctor's handovers, talking to the clinical staff in hospital departments or screening hospital computer systems. Potential

participants are informed about the study by member of the clinical team. If parents are interested in participating in the study, a member of the study team will provide verbal and written information about the study. Medical records will be screened to confirm eligibility for inclusion, either after full consent has been received or with verbal permission from the parent/guardian/legally authorised representative.

RSV point-of-care test

A molecular point-of-care test will be used for the quick identification of RSV in respiratory samples for eligibility to the study, when routine RSV diagnostics have not been performed.

Baseline visit

If RSV infection is confirmed, information will be collected on participant's medical history, any clinical examination performed and any laboratory and radiological investigations that are undertaken as part of routine medical care, and recorded on a case report form (CRF). A standardised respiratory clinical severity score (ReSViNET scale, appendix A (13)) grading the severity of the RSV disease will be calculated at enrolment. Clinical and health economic and quality of life data will be collected. An ARTI diary will be completed for 2 weeks from enrolment (RSV positive infants only).

At enrolment sampling will be done as follows (see also Table 2).

- Respiratory viral flocculated nasopharyngeal swab
- Synthetic absorption matrix [SAM] 2 nasal strips
- Nasopharyngeal bacterial swab
- Venous or capillary blood sample (maximum of ~0.8ml/kg)
- Urine sample (clean catch or from gauze in a nappy)
- Stool sample (from a "dirty" nappy)
- Buccal swab
- If the child is intubated and ventilated: BAL/tracheal aspirate

Subsequent Visits

One week after enrolment (healthy infants only):

One week after enrolment parents of participants will be contacted to assess if their infant developed any illness since enrolment.

Six to eight weeks (convalescent time point) (RSV positive infants only):

At 7 weeks (+/- 1 week) after discharge from hospital/emergency department, or 7 weeks post onset of symptoms for participants not attending hospital, participants will have one follow up visit. This will be a home visit by the study staff. If the child has an ARTI at that moment the follow-up visit will be postponed until the ARTI symptoms have disappeared.

At this time the recent respiratory health will be assessed and the following samples will be taken (see also Table 1):

- Respiratory viral flocculated nasopharyngeal swab
- Synthetic absorption matrix [SAM] 2 nasal strips
- Nasopharyngeal bacterial swab

- Venous or capillary blood sample (maximum of ~0.8ml/kg)
- Urine sample (clean catch or from gauze in a nappy)
- Stool sample (from a “dirty” nappy)
- Buccal swab

Questionnaires

Baseline

- At inclusion a questionnaire about pregnancy, perinatal course and potential risk factors for RSV-hospitalization and sequelae will be filled in

One year of age

- Assessment of respiratory symptoms by parental questionnaire at age 1 year through telephone contact/email/online
- Cost, resource use and Health-Related Quality of Life (HRQoL) data will be collected using questionnaires for caregivers

Two years of age

- Assessment of respiratory symptoms by parental questionnaire at age 2 years through telephone contact/email/online
- Cost, resource use and HRQoL data will be collected using questionnaires for caregivers

Three years of age

- Assessment of respiratory symptoms by parental questionnaire at age 3 years through telephone contact/email/online
- Cost, resource use and HRQoL data will be collected using questionnaires for caregivers

Handling and storage of samples

See table 1 for volume and frequency of sampling. Samples will be stored at the biobank of the UMCU. During the study, samples will be shipped to other laboratories for analysis. Some samples will be sent to laboratories in countries within the European Union (EU) and some samples may be sent to laboratories in countries outside the EU for analysis.

- Sample handling and processing
- Serum: Blood will be drawn into serum collection tubes containing a clot activator and refrigerated between 2°C - 8°C for a maximum of 24 hours. Tubes will be centrifuged at 3000 rpm, 4°C for 10 minutes, serum extracted and stored at -80°C for later analysis.
- Whole blood: Whole blood will be collected in Natrium Heparin tubes and have appropriate buffers added and then be spun down and stored at -80C for later analysis.
- Functional Genomics: Whole blood will be added to Paxgene tubes containing a RNA stabilization reagent and stored at -80°C. Subsequently, RNA will be extracted and gene transcription determined using next generation sequencing approaches.
- Respiratory samples: A bedside RSV test (nasopharyngeal swab) will be carried out prior to enrolment (if no RSV test was done as part of routine clinical care). After enrolment nasopharyngeal swabs will be collected, aliquoted directly into storage tubes and stored at -80°C for later analysis.

- Synthetic absorption matrix [SAM] nasal strips will be collected and stored at -70 to -80°C for later analysis.
- Urine: 3-5 ml of urine will be collected and stored at -70 to -80°C for later analysis.
- Stool: 2-5 ml of stool will be collected and stored at -80°C for later analysis.
- Buccal swab: a buccal swab will be collected and stored at -70 to -80°C for later analysis.

Prioritisation may be required for some of the blood tests (but not other samples) as a result of limited sample volume. We will prioritise serological and transcriptomic analysis but will store whole blood whenever sample volume permits.

All samples will be stored in the UMCU Central Biobank. Participants are being asked separately in the PIF/IC-form whether they give permission for storage of the samples in the biobank and usage of the samples for further research about viral and airway infections according to the biobank regulations. Samples will be stored in the biobank indefinitely.

Table 1. Overview of sampling materials and volumes.

Moment of sampling	Sample	Volume	Analysis (minimum amount)
At inclusion/baseline visit	Serum (venous/capillary)	0.5-2 ml	RSV serology (350-400 µl) Metabolomics (500 µl) Proteome (100 µl)*
	Paxgene (venous/capillary)	0.2-0.5 ml	Transcriptome (200 µl)*
	Whole blood (venous/capillary)	1-2 ml	Cellular immunology*
	Stool	2-5 ml	Microbiome Metagenomics/Metabolomics
	Synthetic absorption matrix [SAM] nasal strip	n/a	Cellular immunology RNA analysis Metagenomics/Metabolomics Mucosal antibodies
	Nasopharyngeal viral swab	3 aliquots of 900 microliter	RSV viral (deep) sequence analysis Multiplex viral PCR
	Nasopharyngeal bacterial swab	4-5 aliquots of 200 microliter	Airway microbiome
	Buccal swab	1 swab	DNA/GWAS
	Urine	3-5 ml	Metabolomics
If ventilated	Broncheo-alveolar aspirate		Cellular immunology RNA analysis

Daily if hospitalized	Nasopharyngeal viral swab	2 aliquots of 1500 microliter	RSV viral load
6-8 weeks after RSV RTI (RSV positive infants only)	Serum (venous/capillary)	1-2 ml	RSV serology (350-400 µl) Metabolomics (500 µl) Proteome (100 µl)*
	Paxgene (venous/capillary)	0.2-0.5 ml	Transcriptome (200 µl)*
	Whole blood (venous/capillary)	1-2 ml	Cellular immunology*
	Stool	2-5 ml	Microbiome Metagenomics/Metabolomics
	Synthetic absorption matrix [SAM] nasal strip	n/a	Cellular immunology RNA analysis Metagenomics/Metabolomics Mucosal antibodies
	Nasopharyngeal viral swab	3 aliquots of 900 microliter	RSV viral (deep) sequence analysis Multiplex viral PCR
	Nasopharyngeal bacterial swab	4-5 aliquots of 200 microliter	Airway microbiome Airway transcriptome
	Buccal swab	1 swab	DNA/GWAS
	Urine	3-5 ml	Metabolomics

* and additional RSV-related biomarkers

2.3. Withdrawal of individual study subjects

Subjects can leave the study at any time for any reason if they wish to do so without any consequences. The investigator can decide to withdraw a subject from the study for urgent medical reasons.

2.3.1. Specific criteria for withdrawal

In addition, the investigator may discontinue a participant from the study at any time if the Investigator considers it necessary for any reason including:

- Ineligibility (either arising during the study or retrospectively having been overlooked at screening)

- Significant protocol deviation
- Withdrawal of Consent
- Loss to follow up

2.4. Replacement of individual subjects after withdrawal

Withdrawn participants will be replaced depending on the moment of withdrawal.

2.5. Follow up of subjects withdrawn from treatment

If the parent/guardian/legally authorised representative withdraws consent, we will analyse any previously collected sample and include their data in further analyses unless they state otherwise.

2.6. Premature termination of the study

The sponsor will notify the METC immediately of a temporary halt of the study, including the reason of such an action. In case the study is ended prematurely, the sponsor will notify the accredited METC within 15 days, including the reasons for the premature termination.

3. Safety reporting

AEs, SAEs and SUSARs

3.1. Temporary halt for reasons of subject safety

Not applicable.

3.2. AEs, SAEs and SUSARs

3.2.1. Adverse events (AEs)

Adverse events are defined as any undesirable experience occurring to a subject during the study, whether or not considered related to [the investigational product / trial procedure/ the experimental intervention]. Because this is a non-interventional, low risk, observational study only SAEs will be registered. Expected AEs directly related to one of the interventions (for example a nose bleed after a nasopharyngeal swab or bruise after a blood test) will not be registered.

3.2.2. Serious adverse events (SAEs)

A serious adverse event is any untoward medical occurrence or effect that

- results in death;
- is life threatening (at the time of the event);
- requires hospitalisation or prolongation of existing inpatients' hospitalisation;
- results in persistent or significant disability or incapacity;
- is a congenital anomaly or birth defect; or
- any other important medical event that did not result in any of the outcomes listed above due to medical or surgical intervention but could have been based upon appropriate judgement by the investigator.

An elective hospital admission will not be considered as a serious adverse event.

Only SAEs directly related to any of the sampling interventions (vene or capillary puncture, collection of buccal and/or nasopharyngeal swabs) will be registered as this is a non-interventional, low risk, observational study.

The investigator will report all SAEs directly related to any of the sampling interventions to the sponsor without undue delay after obtaining knowledge of the events.

The sponsor will report the SAEs through the web portal *ToetsingOnline* to the accredited METC that approved the protocol, within 7 days of first knowledge for SAEs that result in death or are life threatening followed by a period of maximum of 8 days to complete the initial preliminary report. All other SAEs will be reported within a period of maximum 15 days after the sponsor has first knowledge of the serious adverse events.

3.3. Annual safety report

Not applicable.

3.4. Follow up of adverse events

All AEs will be followed until they have abated, or until a stable situation has been reached. Depending on the event, follow up may require additional tests or medical procedures as indicated, and/or referral to the general physician or a medical specialist.

SAEs need to be reported till end of study within the Netherlands, as defined in the protocol.

3.5. Data safety monitoring board (DSMB)

Not DSMB is needed.

4. Statistical analysis

Statistical analysis will be performed by a specialized bioinformatics team.

4.1. Primary study parameter(s)

The primary endpoint is disease severity of RSV infection in the first year of life. The use of biomarkers that are associated with severe RSV infection and respiratory sequelae will be validated. RSV disease severity will be categorized in the following categories: hospitalized non-ventilated, hospitalized ventilated (PICU admitted) and non-hospitalized infants with RSV. If an infant was first recruited in the non-hospitalized group and is admitted during the course of RSV disease, the infant will be changed to the hospitalized non-ventilated or ventilated (PICU admission) group. In addition a control group of healthy controls will be used.

Large data sets are necessary for integrative computational analyses in order to identify profiles associated with disease severity. These data will come in a wide variety of formats depending on the sample being tested and the test being undertaken. In some cases analyses will be undertaken using standard techniques while others may require novel techniques. We will work closely together with other partners in the consortium.

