A critical step in biomarker development is external clinical validation (10) as biomarkers are often identified in data-driven exploratory studies which increase the chance of false positive associations. Therefore, they need to be externally validated to minimise this risk and become acceptable for clinical implementation. This is also part of the regulatory requirements before introduction into routine care. In PROMISE we will establish a clinical study large enough to externally validate the biomarkers identified from RESCEU as well as those that are still being analysed. Gene expression profiles related to neutrophil degranulation as well as innate immunity and antiviral responses will be of specific interest for validation. The most promising candidates will be selected for verification, based on their biological relevance, statistical significance, and potential contribution to a clinical question (if the potential contribution is very small, candidates that did show statistically significance may not be developed further).

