1.2. Objectives

Primary Objective:

- To validate biomarkers that are associated with severe RSV infection and respiratory sequelae.

Secondary Objective(s):

- To analyze dynamics of biomarkers in the upper and lower airways of children with RSV infection and compare these with blood
- To validate currently used case definitions and severity measures for RSV infection in infants

- To determine risk factors for severe RSV disease
- To determine long term sequelae of RSV infection in the first year of life

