1.3. Study design

This will be a monocenter, prospective, observational case-control study conducted across 2 consecutive years in the Wilhelmina Children's hospital and surrounding general practitioner (GP) offices and general hospitals. This case-control study will validate discovered biomarkers related to RSV infection susceptibility and disease severity in the RESCEU case-control study and birth cohort study. In addition, dynamics of the same biomarkers will be analysed in the upper and lower airways to better understand the sources of these biomarker signals. For this a validation cohort of previously healthy infants with different severities of RSV infection will be used and compared to healthy infants.

The following subgroups will be studied:

- Ventilated infants (n=40)
- Hospitalized, non-ventilated infants (n=40)
- Medically attended non-hospitalized infants (n=40)
- Healthy infants (n=40)

Children will be recruited during two RSV seasons. If RSV is suspected but not tested as part of routine care a point of care test for RSV will be done. Samples will be collected within 96 hours after hospitalization or start of symptoms in infants who are not admitted and repeated after 6-8 weeks (convalescence). Healthy infants will be recruited year round. Collection of samples of healthy controls will be done once. There will be annual follow up by questionnaire for up to 3 years.

Blood, stool, buccal, urine and nasopharyngeal samples will be obtained from all RSV positive infants at moment of infection and in convalescence 6-8 weeks later. In ventilated RSV positive infants, bronchoalveolar lavage (BAL) and/or tracheal aspirate samples will be obtained in combination with routine clinical care. Healthy infants will have blood, stool, buccal, urine and nasopharyngeal samples only at enrolment (i.e. there will be no follow up sampling).

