Long-term sequelae (amongst others recurrent wheeze) will be determined using the yearly questionnaires. Results will be displayed as categorical data with percentages or continuous variables with mean (+/-SD) and/or median (interquartile range). Comparisons between groups of different severity (hospitalized non-ventilated, hospitalized ventilated and non-hospitalized infants with RSV) will be performed using chi-square for categorical variables, Student-t-test for normally distributed continuous variables or Mann-Whitney U test for not normally distributed continuous variables.

5. Ethical considerations

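### Respiratory sequelae are in the primary objective but in no biomarker analysis, and section 4.1 describes profile identification where the design calls for validation

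*Protocol*

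**What the plan says.** The primary objective in Protocol section 1.2 is "To validate biomarkers that are associated with severe RSV infection and respiratory sequelae"; the Summary gives the same aim. It therefore names two outcomes.

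Section 2.1.1, repeated in 4.1, sets a single endpoint: "The primary endpoint is disease severity of RSV infection in the first year of life". Section 4.1 then restates the aim: "The use of biomarkers that are associated with severe RSV infection and respiratory sequelae will be validated". Its description of the analysis is: "Large data sets are necessary for integrative computational analyses in order to identify profiles associated with disease severity". On method it adds: "In some cases analyses will be undertaken using standard techniques while others may require novel techniques".

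Section 1.3 gives the sample its role: "For this a validation cohort of previously healthy infants with different severities of RSV infection will be used and compared to healthy infants". Section 1.1 justifies external validation by the risk of false positives when markers come from data-driven exploratory work, and says the study will "externally validate the biomarkers identified from RESCEU as well as those that are still being analysed".

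Sequelae return in section 4.2 item 4: "Long-term sequelae (amongst others recurrent wheeze) will be determined using the yearly questionnaires". They are then compared between the three RSV severity groups with chi-square, t or Mann-Whitney tests. No biomarker enters that comparison.

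**The concern.** There are two mismatches, and the first is the firmer.

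**Sequelae.** The objective promises a result on biomarkers of sequelae. The endpoint does not include sequelae, and the only sequelae analysis has severity group as its explanatory variable. A team that followed section 4 exactly could report whether ventilated infants wheeze more than non-hospitalized ones, but not whether any biomarker is associated with later wheeze.

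**Validation.** Testing a marker fixed in advance and searching a data set for profiles are different analyses with different error properties. Section 4.1 claims the first and describes the second. If a profile were both chosen and assessed in these infants, its performance would be optimistic, and it would still be reported under a validation objective. That is the false-positive problem that section 1.1 gives as the reason for the study.

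**Working it through.** **Step 1. Objective against analyses.** The protocol gives no power, alpha or effect size to reproduce. Its group totals are consistent: 3 × 40 = 120 RSV-positive infants, and 4 × 40 = 160 in all. The main check is textual.

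| Section | Explanatory side | Outcome or contrast | Biomarker related to sequelae? |
|---|---|---|---|
| 4.1 | profiles | severity | no |
| 4.2 item 1 | biomarkers by sample site | within child; severity category | no |
| 4.2 item 2 | case definitions, severity scores | clinical severity data | no |
| 4.2 item 3 | demographic, clinical and laboratory factors | severe disease | no |
| 4.2 item 4 | severity group | sequelae | no |

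No row has a biomarker as predictor and sequelae as outcome. The data for such an analysis will exist: section 2.2.1 plans baseline samples and questionnaires at ages 1, 2 and 3.

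**Step 2. What selection inside the cohort would do (conditional).** This step applies only if markers are chosen with PROMISE data. With n1 = n2 = 40, a pure-noise marker has an AUC centred on 0.5 with

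SD = sqrt((n1 + n2 + 1) / (12 × n1 × n2)) = sqrt(81 / 19,200) = 0.065.

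The expected apparent AUC of the best of m independent noise markers, counting either direction, is 0.5 + 0.065 × E(max |z|), by normal approximation:

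| m (assumed) | E(max \|z\|) | Expected best AUC |
|---|---|---|
| 100 | 2.75 | 0.68 |
| 1,000 | 3.44 | 0.72 |
| 20,000 | 4.18 | 0.77 |

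For comparison, one pre-specified marker at 40 v 40 and two-sided alpha 0.05 (assumed) has 80% power at a standardised difference of (1.96 + 0.84) × sqrt(2/40) = 0.63, an AUC of about 0.67. A selected noise marker could look as good as that. Table 1 plans transcriptome, proteome and metabolomics assays, so large m is plausible. Transcripts are correlated, however, so the figure for 20,000 independent markers is an upper illustration.

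**Step 3. Is a sequelae analysis feasible?** Assume 15% loss, so 120 × 0.85 = 102 infants, and recurrent wheeze in 25% to 35%. For one standardised marker in an unadjusted logistic model, the odds ratio (OR) per SD detectable with 80% power at two-sided 0.05 is exp((1.96 + 0.84) / sqrt(n p (1 − p))):

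- p = 0.25: n p (1 − p) = 19.125, square root 4.37, OR = exp(0.640) = 1.90.
- p = 0.35: n p (1 − p) = 23.205, square root 4.82, OR = exp(0.581) = 1.79.

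Adjustment for severity raises these values, because the candidates are chosen for tracking severity. If severity and age explained 30% of marker variance (assumed), the exponent is divided by sqrt(0.70) = 0.837, giving ORs of about 2.15 and 2.00.

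**The case against.** A reader might infer from 4.1 that the study plans to rediscover markers in its own validation cohort. The text does not go that far. It nowhere says that the profiles are new, and the same section says that biomarkers will be validated. The word profiles also has an earlier use: section 1.1 lists gene expression profiles among the RESCEU discoveries and singles such profiles out for validation. The sentence may be loose wording about handling large omics data. This stands, and it is why the AUC figures above are conditional.

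A reader might also infer that the candidate set is open to PROMISE results. The markers still under analysis are most naturally RESCEU markers, since section 1.4.4 says that the RESCEU samples are still being worked on. Such markers remain external to PROMISE. Section 1.1 also gives selection criteria, and section 1.4.4 describes an independent sample as the ideal. What the protocol lacks is a point at which the list closes.

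Model coefficients, cut-offs, performance measures and calibration commonly belong in a statistical analysis plan, which is not at hand. Their absence is not part of this point.

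On sequelae, it can be said that the data are collected anyway, so an analysis could be added without new visits. That is true and lowers the cost of the correction. It does not remove the mismatch between a two-part primary objective and a severity-only endpoint, and no section of the protocol closes it.

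**Conclusion.** The sequelae mismatch holds on the text. Sequelae stand in the primary objective, severity is the only primary endpoint, and no analysis in this protocol relates a biomarker to sequelae. An unseen analysis plan might contain one, but it should not have to repair the pairing of objective and endpoint.

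The validation mismatch holds in a narrower form: 4.1 states validation as the aim and describes only identification of profiles. The apparent AUC of 0.68 to 0.77 from noise alone shows what selection in PROMISE would risk. It rests on independent markers, assumed marker counts and the condition that selection happens there. It does not predict what the study will report.

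A sequelae analysis is feasible but only for fairly strong markers, with an OR per SD of about 1.8-1.9 unadjusted and more with severity adjustment. This rests on the assumed 15% loss and 25-35% wheeze.

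This should be fixed. It concerns the primary objective, but the study is observational, the data are collected either way, and the correction is mainly to wording.

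**What to change.** 1. **Sequelae.** Do one of the following. Either add to section 4 a regression of recurrent wheeze (yearly questionnaires to age 3) on each RESCEU candidate biomarker measured at baseline, in RSV-positive infants, adjusted for age at infection; give further adjustment for severity group as a separate analysis, because it asks about prediction beyond severity. Or move sequelae from the primary to a secondary objective, in the Summary and in sections 1.2, 2.1.1 and 4.1.
2. **Validation.** State in 4.1 that the primary analysis tests a dated list of RESCEU-derived candidates, fixed before PROMISE assay data are linked to severity group. State also that any profile identified or refitted in PROMISE is exploratory.

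The cost is a protocol amendment and a dated candidate list, with no new samples, visits or questionnaires. The downside is that RESCEU markers that mature after the list is fixed can be reported only as exploratory.
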